## LIST OF ABBREVIATIONS AND DEFINITIONS OF TERMS

Abbreviation	Term
ACS	Abnormal, Clinically Significant
AE	Adverse Event
AIC	Akaike's Information Criterion
AIMS	Abnormal Involuntary Movement Scale
ALP	Alkaline Phosphatase
ALT	Alanine Transaminase
ANCOVA	Analysis of Covariance
ANCS	Abnormal, Not Clinically Significant
AR(1)	Autoregressive (1)
ARH(1)	Autoregressive, Heterogeneous (1)
AST	Aspartate Transaminase
BARS	Barnes Akathisia Rating Scale
BMI	Body Mass Index
CDSS	Calgary Depression Scale for Schizophrenia
CGI-S	Clinical Global Impression – Severity of Illness Scale
CGI-I	Clinical Global Impression - Improvement Scale
CI	Confidence Interval
СМН	Cochran Mantel Haenszel
C-SSRS	Columbia-Suicide Severity Rating Scale
CS	Compound Symmetry
CSH	Compound Symmetry, Heterogeneous
DBP	Diastolic Blood Pressure
DMC	Data Monitoring Committee
ECG	Electrocardiogram
eCRF	Electronic Case Report Form
EPS	Extrapyramidal Symptoms
ET	Early Termination
FA0(q)	No Diagonal Factor Analytic covariance structure (with q equal to the number of
	time points)
FAS	Full Analysis Set
FDA	Food and Drug Administration
ISSR	Interim Sample Size Recalculation
ITT	Intent-to-Treat
IVRS	Interactive Voice-Activated Response System
IWRS	Interactive Web-based Response System
LSM	Least Squares Mean
MAR	Missing at Random
МСМС	Markov Chain Monte Carlo
Document: \\quintil	les.net\Enterprise\Apps\sasdata\SASb\SAS\Noven\HP-

6\_18Jan2018.docx Author: [name] Version Number: Version Date:

Template No: CS\_TP\_BS016 – Revision 3 Effective Date: 01May2012 Reference: CS\_WI\_BS005

Final 6

18Jan2018

Copyright © 2012 Quintiles Transnational Corp. All rights reserved.

Noven Pharmaceuticals, Inc. STATISTICAL ANALYSIS PLAN: PROTOCOL HP-3070-GL-04 Page 9 of 50

MedDRA	Medical Dictionary for Regulatory Activities
MI	Multiple Imputation
MMRM	Mixed Model for Repeated Measures
MNAR	Missing Not at Random
MSQ	Medication Satisfaction Questionnaire
NCI CTCAE	National Cancer Institute Common Terminology Criteria for Adverse Events
PANSS	Positive and Negative Syndrome Scale
PAS	Pharmacokinetic Analysis Set
РК	Pharmacokinetic
PT	Preferred Term
SAE	Serious Adverse Event
SAF	Safety Analysis Set
SAP	Statistical Analysis Plan
SAS	Simpson-Angus Scale
SAS	Statistical Analysis Software
SBP	Systolic Blood Pressure
SD	Standard Deviation
SI	Standard International
SL	Sublingual
SOC	System Organ Class
SSR	Sample Size Recalculation
TEAE	Treatment-Emergent Adverse Event
TOEP	Toeplitz (covariance structure)
ТОЕРН	Toeplitz, Heterogeneous (covariance structure)
ULN	Upper Limit Of Normal
WHO-DD	World Health Organization Drug Dictionary

Document:	ent: \\quintiles.net\Enterprise\Apps\sasdata\SASb\SAS\Noven\HP-		
	3070\XWA17541\Biostatistics\Docur	mentation\SAP\Final 6\Noven HP-3070-GL-04 SA	AP text Final
	6_18Jan2018.docx		
Author:	[name]	Version Number:	Final 6
		Version Date:	18Jan2018
Template No:	CS_TP_BS016 – Revision 3	Reference: C	CS_WI_BS005

Template No: CS\_TP\_BS016 – Revision 3 Effective Date: 01May2012

Noven Pharmaceuticals, Inc. STATISTICAL ANALYSIS PLAN: PROTOCOL HP-3070-GL-04 Page 10 of 50

## **1. INTRODUCTION**

This document describes the rules and conventions to be used in the presentation and analysis of efficacy and safety data for Protocol HP-3070-GL-04. It describes the data to be summarized and analyzed, including specifics of the statistical analyses to be performed.

This statistical analysis plan (SAP) is based on protocol version 3 dated 21 November 2016.

# 2. STUDY OBJECTIVES

## 2.1. PRIMARY OBJECTIVE

The primary objective of the study is to evaluate efficacy of HP-3070 compared with placebo for the treatment of schizophrenia as evaluated by Positive and Negative Syndrome Scale (PANSS) total score.

## **2.2. KEY SECONDARY OBJECTIVES**

Key Secondary Efficacy Objective:

• Clinical Global Impression – Severity of Illness Scale (CGI-S)

## **2.3.** OTHER SECONDARY OBJECTIVES

Other Secondary Efficacy Objectives: To evaluate the efficacy of HP-3070 using the following measures:

- PANSS total score at each timepoint
- Clinical Global Impression Severity of Illness Scale (CGI-S) at each timepoint
- Clinical Global Impression Improvement Scale (CGI-I) at each timepoint
- Proportion of CGI-I responders at each timepoint
- Positive, negative, and general pathology subscores of PANSS
- Proportion of PANSS responders; At each time point (Weeks 1 6), subjects having a 30% or greater improvement from baseline in PANSS total score will be defined as responders
- Calgary Depression Scale for Schizophrenia (CDSS)
- Medication Satisfaction Questionnaire (MSQ) score

Document:	\\quintiles.net\Enterprise\Apps\sasdata\SASb\SAS\Noven\HP-			
	3070\XWA17541\Biostatistics\Docu	imentation\SAP\Final 6\Noven HP-3070-GL-04 S	AP text Final	
	6_18Jan2018.docx			
Author:	[name]	Version Number:	Final 6	
		Version Date:	18Jan2018	
Template No:	CS TP BS016 – Revision 3	Reference:	CS WI BS005	

Template No: CS\_TP\_BS016 – Revision 3 Effective Date: 01May2012

Copyright © 2012 Quintiles Transnational Corp. All rights reserved.

Noven Pharmaceuticals, Inc. STATISTICAL ANALYSIS PLAN: PROTOCOL HP-3070-GL-04 Page 11 of 50

# 2.4. SAFETY OBJECTIVES

Safety objectives are to evaluate the safety and tolerability of HP-3070 compared with placebo, including:

- Adverse events (AEs), including treatment-emergent AEs (TEAEs), AEs leading to discontinuation from the study drug, serious adverse events (SAEs), and deaths
- Change from Baseline in clinical laboratory results (including prolactin, fasting glucose, and lipids), ECG results, body weight, and vital signs
- Results of C-SSRS, BARS, AIMS, and SAS
- Dermal safety

## **2.5. EXPLORATORY OBJECTIVES**

Exploratory objectives are to assess the impact of covariates on asenapine exposure using a model-based approach and to explore the exposure-response relationship with relevant endpoints.

## 3. STUDY DESIGN

## **3.1. GENERAL DESCRIPTION**

This is a Phase 3, randomized, double-blind, placebo-controlled, in-patient, safety, and efficacy study to evaluate HP-3070 for the treatment of schizophrenia.

This study will consist of a Screening/placebo Run-in Period of 3 to 14 days, a 6-week double-blind Treatment Period and a 30 day Follow-up Period.

Subjects will be hospitalized at the Screening Visit and will remain hospitalized during the study. The subject may leave the hospital study for necessary personal business. Any subject who leaves the site must have an alcohol breathalyzer and urine drug tests when they return to the site.

After obtaining informed consent, each subject will be assigned a unique subject number. Eligible subjects will be hospitalized for the duration of the study. While undergoing screening procedures and waiting for results of laboratory tests, ECGs, and other assessments, the subject will start treatment with the single-blind placebo patch. The subject must have the single-blind placebo patch applied for a minimum of 3 days prior to being randomized into the double-blind Treatment Period. In addition, current antipsychotic and other prohibited medications will be washed out during the run-in period and must be completed prior to randomization into the double-blind treatment period. Details in regard to wash-out periods for specific drugs are summarized in Protocol Section 5.10.1. Subjects who have a decrease in PANSS total score ≥20% from Screening to Baseline or a PANSS total score <80 at Screening or Baseline will be discontinued from the study and will not enter the double-blind Treatment Period.

Document:	\\quintiles.net\Enterprise\Apps\sasdata\SASb\SAS\Noven\HP-			
Documenti	3070\XWA17541\Biostatistics\Docu	imentation\SAP\Final 6\Noven HP-3070-GL-04 S/	AP text Final	
	6_18Jan2018.docx			
Author:	[name]	Version Number:	Final 6	
		Version Date:	18Jan2018	
Template No:	CS TP BS016 – Revision 3	Reference: C	CS WI BS005	

Effective Date: 01May2012

Copyright © 2012 Quintiles Transnational Corp. All rights reserved.

Noven Pharmaceuticals, Inc. STATISTICAL ANALYSIS PLAN: PROTOCOL HP-3070-GL-04 Page 12 of 50

Subjects eligible for randomization into the double-blind Treatment Period will be randomly assigned to HP-3070 9.0 mg, HP-3070 18.0 mg, or placebo in a 1:1:1 ratio stratified by country. Subjects will receive treatment with study medication daily for 6 weeks.

The study will evaluate 9.0mg (HP-3070 9.0 mg) and 18.0 mg (HP-3070 18.0 mg) of HP-3070 transdermal patches versus placebo transdermal patches. Patches will be applied by site personnel at approximately the same time daily and each patch will be worn for 24 hours. Every day, 24 hours (±15 minutes) after patch application, site personnel will remove previous day's patches and apply new patches.

All subjects will have a follow-up contact (site visit or telephone call, at the discretion of the Investigator) 30 days after the last patch is removed. This contact will be used to collect information about any Adverse Events (AEs) or Serious Adverse Events (SAEs) that may have occurred since discharge and to follow-up on any Adverse Events (AEs) that were on-going at discharge.

Assuming an effect size of 0.35 on the change in PANSS total score from baseline to Week 6 for the two pairwise comparisons between each active HP-3070 treatment arm and placebo, the power for detecting a statistically significant HP-3070 advantage will be approximately 0.90 having 204 evaluable subjects per each treatment arm, using a two-sided alpha level of 0.025 for each comparison. A two-sided overall type I error is equal to 0.05. Having three treatment arms, the total number of subjects randomized in the trial and included in primary analysis set will be approximately 612.

The effect size of 0.35 (difference between means equal to 7 and common standard deviation (SD) equal to 20) was chosen based on the lowest effect size observed in results from the studies conducted with sublingual (SL) asenapine and approved by the Food and Drug Administration (FDA) (Sycrest®/SAPHRIS® [Study 041004, and Study 041023]).

A sample size recalculation (SSR) will be conducted as described in Section 4.2 on the blinded data after approximately 50% of the originally planned number of subjects have been randomized and completed up to 6 weeks of study treatment.

## **3.2.** SCHEDULE OF EVENTS

In this study, efficacy will be evaluated using widely accepted, standard questionnaires. These include the PANSS, CGI-S, CGI-I, CDSS and MSQ.

In addition to standard safety measures (AEs, clinical laboratory assessments, vital signs, weight, electrocardiogram [ECG] results), this study will also include assessments of extrapyramidal symptoms (EPS) symptoms using the Simpson-Angus Scale (SAS), Barnes Akathisia Rating Scale (BARS), and Abnormal Involuntary Movement Scale (AIMS). Suicidality will be monitored using the Columbia-Suicide Severity Rating Scale (C-SSRS). Patch adhesion will be assessed at specified timepoints. Dermal safety will be assessed by daily evaluation of irritation at the site of patch application and by a review of any dermal reactions reported as AEs.

The schedule of study procedures and assessments is presented in Protocol Table 1.

Document:	\\quintiles.net\Enterprise\Apps\sasdata\SASb\SAS\Noven\HP- 3070\XWA17541\Bigstatistics\Documentation\SAP\Einal 6\Noven HP-3070-GL-04 SAP text Einal		
	6_18Jan2018.docx		
Author:	[name]	Version Number:	Final 6
		Version Date:	18Jan2018
Template No:	CS_TP_BS016 – Revision 3	Reference: 0	CS_WI_BS005

Copyright © 2012 Quintiles Transnational Corp. All rights reserved.

Effective Date: 01May2012

Noven Pharmaceuticals, Inc. STATISTICAL ANALYSIS PLAN: PROTOCOL HP-3070-GL-04 Page 13 of 50

## **3.3.** CHANGES TO ANALYSIS FROM PROTOCOL

There are no changes to analysis from protocol.

#### 4. PLANNED ANALYSES

The following analyses will be performed for this study:

- Blinded Sample Size Recalculation
- Final Analysis

## 4.1. DATA MONITORING COMMITTEE (DMC)

There will be no DMC for this study.

## 4.2. BLINDED SAMPLE SIZE RECALCULATION

Sample size recalculation (SSR) will be conducted on the blinded data after approximately 50% of the desired number of patients have been randomized and completed up to 6 weeks of study treatment. This SSR will be directed and conducted by an independent statistician from IQVIA, who is not involved in the trial conduct other than this SSR.

The purpose of this SSR is to assess the assumption regarding the standard deviation made for sample size calculation for the primary endpoint. No other information will be generated as part of the SSR.

This SSR will not be conducted with an intention of decreasing the original sample size or stopping the trial early.

An assumed treatment effect size of 0.35 which served as basis for the original sample size calculation corresponds to an assumption of mean difference of 7 in the change in PANSS total score from Baseline to Week 6 between each HP-3070 treatment group and placebo and a common standard deviation of 20. The independent statistician will estimate a pooled standard deviation from blinded data at the time of SSR analysis as follows:

$$SD_{pooled} = \sqrt{\frac{1}{N_{SSR} - 1} \left[ \sum_{i=1}^{N_{SSR}} (x_i - \bar{x})^2 \right]}$$

where  $N_{SSR}$  is the total number of subject with change in PANSS total score from Baseline to Week 6 available at the time of SSR analysis,  $x_i$  are the changes from baseline values of these subjects, and  $\bar{x}$  is the grand mean of the pooled sample. Based on the re-estimated  $SD_{pooled}$  and using the same assumptions for all other aspects of sample size calculation as postulated for the original sample size estimation, the independent statistician will

Document:	\\quintiles.net\Enterprise\Apps\sa	sdata\SASb\SAS\Noven\HP-	
	3070\XWA17541\Biostatistics\Doc	umentation\SAP\Final 6\Noven HP-3070-GL-04 S	AP text Final
	6_18Jan2018.docx		
Author:	[name]	Version Number:	Final 6
		Version Date:	18Jan2018
Template No:	CS TP BS016 – Revision 3	Reference: (	CS WI BS005

Effective Date: 01May2012

Copyright © 2012 Quintiles Transnational Corp. All rights reserved.

Noven Pharmaceuticals, Inc. STATISTICAL ANALYSIS PLAN: PROTOCOL HP-3070-GL-04 Page 14 of 50

recommend either to keep the original sample size or to increase it in order to maintain a desired level of power. The final decision with regard to sample size will be at the discretion of the Sponsor upon review of the independent statistician's recommendation based on the estimated pooled standard deviation and its impact on the power of the study. The decision will be reported in a separate document.

The table below provides examples of different scenarios corresponding to various estimated values of  $SD_{pooled}$  and possible corresponding sample size increases.

SD pooled	Sample Size per Arm*	Sample Size Increase per Arm**	Power if Original Sample Size Maintained
20.0	204	Not applicable (Original)	90%
20.5	215	11	88%
21.0	225	21	86%
21.5	236	32	85%
22.0	247	43	83%
22.5	258	54	81%
23.0	270	66	79%
23.5	282	78	77%
24.0	294	90	75%
24.5	306	102	73%
25.0	318	114	71%
25.5	331	127	69%
26.0	344	140	68%
26.5	358	154	66%
27.0	371	167	64%

\* Sample size (per arm) required to attain 90% power.

\*\* Sample size increase (per arm) required to maintain 90% power.

Note: Sample size calculations are based on assumed mean difference of 7 between each HP-3070 treatment group and placebo and a 2-sided t-test at the 0.025 significance level.

With the procedure for re-estimation of pooled standard deviation and re-calculation of sample size in a blinded manner, no Type I Error adjustment is necessary (Kieser and Friede, 2003).

#### 4.2.1. SAMPLE SIZE RECALCULATION DOCUMENTATION

Additional details of the sample size recalculation can be found in the SSR SAP version 1, dated July 7th, 2017. The sample size recalculation was conducted according to the SSR SAP on July 10th, 2017. The conclusion of the sample size recalculation analysis is documented in the Interim Sample Size Recalculation (ISSR) Study report dated July 27th, 2017.

Document:	\\quintiles.net\Enterprise\Apps\sasdata\SASb\SAS\Noven\HP-			
	3070\XWA17541\Biostatistics\Doc	cumentation\SAP\Final 6\Noven HP-3070-GL-04 S	AP text Final	
	6_18Jan2018.docx			
Author:	[name]	Version Number:	Final 6	
		Version Date:	18Jan2018	
Template No:	CS TP BS016 – Revision 3	Reference: 0	CS WI BS005	

Effective Date: 01May2012

Copyright © 2012 Quintiles Transnational Corp. All rights reserved.

Noven Pharmaceuticals, Inc. STATISTICAL ANALYSIS PLAN: PROTOCOL HP-3070-GL-04 Page 15 of 50

# 4.3. FINAL ANALYSIS

All final, planned analyses identified in this SAP will be performed by IQVIA Biostatistics following Sponsor Authorization of this Statistical Analysis Plan, Database Lock, Sponsor Authorization of Analysis Sets and Unblinding of Treatment. The final analysis will include a set of patient profiles to be presented in the final report as patient narratives. These profiles will be included for subjects who reported serious adverse events, treatment emergent adverse events leading to study discontinuation, or adverse events of EPS.

# 5. ANALYSIS SETS

Sponsor agreement and authorization of subjects included/ excluded from each analysis set will be obtained prior to the unblinding of the study.

# 5.1. ALL SUBJECTS SCREENED SET

The all subjects screened set will contain all subjects who provide informed consent for this study. This analysis set will be used for run-in period demographic and disposition summaries and will be based on data collected in the Interactive Voice Activated Response System (IVRS)/Interactive Web-based Response System (IWRS).

## 5.2. INTENT-TO-TREAT ANALYSIS SET

Intent-to-Treat (ITT) Analysis Set includes all consented and randomized subjects. Regardless of any protocol deviations, analyses performed on the ITT set will be based on the randomized treatment assignment and all available data.

## 5.3. FULL ANALYSIS SET

Full Analysis Set (FAS) includes all randomized subjects who have had at least 1 patch of double-blind study medication applied and who have a Baseline PANSS total score and at least 1 post-Baseline assessment of the primary efficacy measure (PANSS total score). The FAS will be used as the primary set for analysis of efficacy endpoints based on randomized treatment assignment.

## 5.4. SAFETY ANALYSIS SET

The Safety Analysis Set (SAF) includes all subjects who have had at least 1 patch of double-blind study medication applied and who have at least 1 post-dose safety measurement during the double-blind treatment period. In the unlikely event that errors may have occurred in treatment arm assignments, then analyses using the SAF will

Document:	ent: \\quintiles.net\Enterprise\Apps\sasdata\SASb\SAS\Noven\HP-			
	3070\XWA17541\Biostatistics\Docu	mentation\SAP\Final 6\Noven HP-3070-GL-04 S	AP text Final	
	6_18Jan2018.docx			
Author:	[name]	Version Number:	Final 6	
		Version Date:	18Jan2018	
Template No:	CS_TP_BS016 – Revision 3	Reference: C	CS_WI_BS005	
Effective Date	: 01May2012			

Copyright © 2012 Quintiles Transnational Corp. All rights reserved.

Noven Pharmaceuticals, Inc. STATISTICAL ANALYSIS PLAN: PROTOCOL HP-3070-GL-04 Page 16 of 50

be based on treatment actually received. The SAF will be used for the analysis of dermal evaluations and safety endpoints.

# 5.5. PHARMACOKINETIC ANALYSIS SET

The Pharmacokinetic Analysis Set (PAS) includes all subjects who have at least one dose of study medication during the double blind treatment period and have at least one blood sample for pharmacokinetic (PK) assessment. Subjects may be excluded from the PAS set if they significantly violate inclusion or exclusion criteria, significantly violate the protocol in a way that may influence the PK analysis, if any unexpected error occurs during the study that may influence the PK analysis (e.g., early detachment of transdermal systems, apparent sample switching, etc.) or if their data are unavailable or incomplete. The PAS will be used for the analysis with model based approach as well as for the presentation of descriptive summaries of PK data. Excluded cases will be documented together with the reason for exclusion.

Analysis dataset for pharmacokinetic assessments will be created by Metrum Research Group, LLC.

# **6.** GENERAL CONSIDERATIONS

# 6.1. REFERENCE START DATE AND STUDY DAY

Study Day during the run-in period and during the double blind treatment period will be calculated from the reference start date, and will be used to show start/ stop day of assessments and events.

Reference start date during the double blind treatment period is defined as the day of the first dose of study medication, (Day 1 is the day of the first dose of double-blind study medication), and will appear in every listing where an assessment date or event date appears.

Reference start date during the run-in period is defined as the day of the first dose of study medication during the run-in period.

• If the date of the event is on or after the reference date then:

Study Day = (date of event – reference date) + 1.

• If the date of the event is prior to the reference date then:

Study Day = (date of event – reference date).

In the situation where the event date is partial or missing, Study Day, and any corresponding durations will appear partial or missing in the listings.

Document:	\\quintiles.net\Enterprise\Apps\sasdata\SASb\SAS\Noven\HP-			
	3070\XWA17541\Biostatistics\Doc	umentation\SAP\Final 6\Noven HP-3070-GL-04 S/	AP text Final	
	6_18Jan2018.docx			
Author:	[name]	Version Number:	Final 6	
		Version Date:	18Jan2018	
Template No:	CS TP BS016 – Revision 3	Reference: C	S WI BS005	

Effective Date: 01May2012

Copyright © 2012 Quintiles Transnational Corp. All rights reserved.

Noven Pharmaceuticals, Inc. STATISTICAL ANALYSIS PLAN: PROTOCOL HP-3070-GL-04 Page 17 of 50

# 6.2. BASELINE

Unless otherwise specified, baseline is defined as the last non-missing measurement taken prior to or on the date of first dose of double-blind study medication (including unscheduled assessments). For assessments done on the date of first double-blind study medication dose, if time of measurement is available, it will be compared to the date and time of the first double-blind dose of study medication to determine if the measurement is pre-dose (baseline) or post-dose (post-baseline).

## 6.3. DERIVED TIME POINTS

Early Termination (ET) visit information that is collected post-Baseline will be assigned to the next scheduled visit. This will apply to all data points used in efficacy and safety analysis. For each type of assessment, the ET visit data will be assigned to the next scheduled visit when that type of assessment is planned to be collected. The purpose for this derivation is to include ET assessments in the summary tables and listings.

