## 6.5. WINDOWING CONVENTIONS

There will be no visit windowing for this protocol. All data will be organized and analysed according to the scheduled times as outlined in the protocol and by the visit denoted on the electronic Case Report Form (eCRF). Early termination visit information will be handled as described in Section 6.3.

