# 7.3. MISSING DATA

In the calculation of total and subscale scores, missing individual items used in the derivations of aggregate scores will be handled as described in the sections defining the corresponding variables, in accordance with a scoring manual for each scale.

Missing endpoint values in this study may result from patients discontinuing from the study prematurely or

	6 19 Jan 2019 docx		
	6_18Jan2018.00CX		
Author:	[name]	Version Number:	Final 6
		Version Date:	18Jan2018
Template No: CS_TP_BS016 – Revision 3		Reference: CS_WI_BS005	

Effective Date: 01May2012

Copyright © 2012 Quintiles Transnational Corp. All rights reserved.

Noven Pharmaceuticals, Inc. STATISTICAL ANALYSIS PLAN: PROTOCOL HP-3070-GL-04 Page 19 of 50

missing intermediate assessments while remaining on study. For primary analysis of the primary endpoint and other efficacy endpoints, missing observations will not be imputed. The primary analysis method for continuous endpoints will be based on a mixed model with repeated measures (MMRM) which utilizes all available data (complete and partial) from subjects included in an analysis set. The MMRM-based approach assumes that data are missing at random (MAR). MAR refers to a missingness mechanism that is independent of missing responses, conditionally on observed response history and covariates. This assumption inherently implies that the treatment effect is similar for those who discontinue prematurely and for those who complete the study in their respective treatment arms.

Sensitivity analyses to investigate robustness to missing data will be performed for the primary endpoint as described in Section 15.1.4, and key secondary endpoint as described in Section 15.2.3.

For analysis of categorical efficacy endpoints, such as PANSS responders based on percent improvement from baseline, subjects discontinuing from the study prematurely or missing intermediate measurements will be considered as non-responders.

Missing safety data will not be imputed.

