Copyright © 2012 Quintiles Transnational Corp. All rights reserved.

Effective Date: 01May2012

Noven Pharmaceuticals, Inc. STATISTICAL ANALYSIS PLAN: PROTOCOL HP-3070-GL-04 Page 27 of 50

in PANSS total score as the repeated dependent variable, with country, treatment (HP-3070 9 mg, HP-3070 18 mg, and placebo), visit (Weeks 1, 2, 3, 4, 5, and 6), treatment by visit interaction, and the Baseline PANSS total score as covariates. An unstructured covariance matrix will be assumed. In the event the convergence cannot be attained with the unstructured correlation matrix, the following alternative structures will be attempted in the specified order (from least restrictive to most restrictive): heterogeneous Toeplitz structure (TOEPH), heterogeneous autoregressive(1) (ARH(1)), heterogeneous compound symmetry (CSH), No Diagonal Factor Analytic (FA0(q), with q equal to the number of time points), Toeplitz structure (TOEP), autoregressive(1) (AR(1)), and compound symmetry (CS). The first structure in this list with which the model converges will be used. If either ARH(1) or AR(1) structure is used, a random subject intercept will also be included in the model. The Restricted Maximum Likelihood (REML) method will be used for the estimation of the covariance parameters. The Kenward-Rogers method will be used to estimate the denominator degrees of freedom. The treatment-by-time interaction term allows for comparisons of the treatment groups at each time point. Treatment comparisons of each HP-3070 dose to placebo at Week 6 will be used for the primary analysis.

SAS procedure MIXED will be used to perform this analysis as follows:

proc mixed data=<analysis dataset>;

class TRT COUNTRY VISIT SUBJID; model CHG = TRT COUNTRY VISIT TRT\*VISIT BASE / ddfm=kr; repeated VISIT / type=un subject=SUBJID; Ismeans TRT\*VISIT / cl pdiff=all;

run;

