In order to perform an ANCOVA on rank-transformed data, changes from Baseline to Week 6 in the PANSS total score will be transformed to ranks as described in Appendix 4. Before performing the rank transformation, subjects with missing data at Week 6 will be imputed with a change from baseline equal to the worst (largest) change from baseline in observed data plus 1 for informative cases following pattern 1, so that these subjects would have the worst (highest) rank after the transformation. (It should be noted that with an assignment of the highest rank to subjects with missing data, the rank-based ANCOVA, contrary to the primary analysis, does not assume a MAR mechanism, but rather implies the worst outcome for all early discontinued subjects regardless of treatment arm). The details of the rank-based ANCOVA are described in Appendix 4.

Sensitivity analysis to investigate impact of outliers on primary efficacy: To investigate the impact of outliers on the primary efficacy analysis, a sensitivity analysis will be performed by including outliers.

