	6_18Jan2018.docx		
Author:	[name]	Version Number:	Final 6
		Version Date:	18Jan2018
Template No:	CS_TP_BS016 - Revision 3	Reference: (	S WL BS005

Effective Date: 01May2012

Copyright © 2012 Quintiles Transnational Corp. All rights reserved.

Noven Pharmaceuticals, Inc. STATISTICAL ANALYSIS PLAN: PROTOCOL HP-3070-GL-04 Page 31 of 50

passive/apathetic social withdrawal, difficulty in abstract thinking, lack of spontaneity and flow of conversation, stereotyped thinking.

If one or more items in the subscale are missing at a given assessment, the subscale score will be set to missing.

#### 15.3.1.7. Change from Baseline in PANSS General Psychopathology Subscale at Weeks 1 through 6

PANSS General Psychopathology Subscale is a sum of 16 items: somatic concern, anxiety, guilt feelings, tension, mannerisms and posturing, depression, motor retardation, uncooperativeness, unusual thought content, disorientation, poor attention, lack of judgment and insight, disturbance of volition, poor impulse control, preoccupation, and active social avoidance.

If one or more items in the subscale are missing at a given assessment, the subscale score will be set to missing.

# 15.3.1.8. PANSS Responder Based on ≥30% Improvement from Baseline in PANSS total score at Weeks 1 through 6

At each time point, subjects having a 30% or greater improvement from baseline in PANSS total score will be defined as "responders".

The PANSS total score percentage change will be defined as (Value at Week X – Baseline value) X 100 / (Baseline value).

The responder indicator will be set to 1 if the percentage change is less than or equal to -30% and set to 0 if the percentage change is greater than -30% or missing.

# 15.3.1.9. PANSS Responder Based on >=X% Improvement from Baseline in PANSS total score at Week 6

At Week 6, responder status will be derived in a similar way as described in section 15.3.1. 8 at different levels of required percent improvement from baseline where X=5% to 100% with 5% increments.

A continuous responder analysis will be performed based on these derivations as described in Section 15.3.3.3.

#### 15.3.1.10. Change from Baseline in CDSS Score at Weeks 1 through 6

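### The early-termination shift in SAP 6.3 lets subjects who discontinue between visits be responders at the next visit, or keep an observed rank at Week 6, contradicting SAP 7.3 and 15.1.4

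*SAP*

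**What the plan says.** **The shift.** SAP 6.3: "Early Termination (ET) visit information that is collected post-Baseline will be assigned to the next scheduled visit". On scope it adds: "This will apply to all data points used in efficacy and safety analysis". On purpose it adds: "The purpose for this derivation is to include ET assessments in the summary tables and listings". Section 6.5 sets no visit windows and refers back: "Early termination visit information will be handled as described in Section 6.3".

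**Responder rules.** Section 7.3, on categorical efficacy endpoints: "subjects discontinuing from the study prematurely or missing intermediate measurements will be considered as non-responders". Section 15.3.1.8 sets the indicator to 1 at a percentage change of -30% or lower; it is "set to 0 if the percentage change is greater than -30% or missing". Section 15.3.1.9 derives the other thresholds in the same way. Section 15.3.2 makes a subject a non-responder at a time point when the value at that time point is missing. It does not mention discontinuation.

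**Rank ANCOVA.** Section 15.1.4, Scenario #4, gives the worst observed change plus 1 to subjects whose Week 6 value is missing. The footnotes to shell Tables 14.2.1.2.6 and 14.2.2.8 repeat that condition. The explanatory sentence in the same paragraph says the method "implies the worst outcome for all early discontinued subjects regardless of treatment arm".

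**Schedule.** Section 15.1.3 models PANSS at "visit (Weeks 1, 2, 3, 4, 5, and 6"), and says every discontinued subject has a PANSS assessment at the time of discontinuation.

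**The concern.** The responder analyses and the rank ANCOVA are described as counting discontinuation against the subject. Once an early-termination score has been moved to the next visit, that visit is no longer missing, and the rules that should count it as failure do not apply. Two programmers, one working from 7.3 and one from 15.3.1.8 with 15.3.2, would produce different responder counts and p-values from the same data. If the text is not settled beforehand, the choice could be made after unblinding.

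The outputs affected matter. The continuous responder analysis and the rank ANCOVA are Scenarios #2 and #4 of the sensitivity analyses for the primary endpoint, and 15.2.3 carries the sensitivity analyses over to CGI-S. The 30% PANSS and CGI-I responder endpoints are tested by CMH at every week (15.3.3.2). The rank analysis is presented as a departure from missing at random, and as written it exempts the latest dropouts.

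**Working it through.** **1. Trace one subject.** The subject stops after the Week 5 visit and before Week 6. The early-termination PANSS shows 35% improvement, and there has been no switch to another antipsychotic.

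- The score exists, because 15.1.3 requires a PANSS at discontinuation.
- The outlier rule in 15.1.3 does not remove it. That rule needs both more than 24 hours since stopping and a switch to an approved antipsychotic.
- PANSS is weekly, so 6.3 makes the score the Week 6 value.

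| Analysis | 6.3 plus the operative rule | The other statement |
|---|---|---|
| PANSS responder, Week 6 | Change of -35% is at or below -30% and not missing: responder (15.3.1.8, 15.3.2) | Discontinued prematurely: non-responder (7.3) |
| Rank ANCOVA, Week 6 | Week 6 not missing: rank of the observed score (15.1.4) | Early discontinuation: worst outcome (15.1.4, explanatory sentence) |

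The same holds for responder status at earlier visits. A subject who stops between Weeks 2 and 3 can be a Week 3 responder; from Week 4 on the values are missing and the rules agree again. The rank analysis uses Week 6 only, so there the conflict concerns those who stop after Week 5.

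**2. The planned arm size.** SAP 3.1 gives a difference of 7, SD 20, two-sided alpha 0.025 and 204 evaluable subjects per arm for about 90% power. A two-sample t-test calculation gives 204 per arm with power 0.9002, so the figure reproduces. The point does not affect it; 204 is used below only as a denominator.

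**3. Size under assumed rates.** The SAP gives no dropout rate, dropout timing or early-termination response rate. Let *d* be the share of an arm that stops between Weeks 5 and 6, and *r* the share of those whose early-termination score meets the 30% cut. Both are assumptions.

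- Subjects reclassified as observed at Week 6: 204 × *d*
- Extra Week 6 responders: 204 × *d* × *r*
- Shift in the arm's responder rate, in percentage points: 100 × *d* × *r*

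| *d* | Subjects per arm | Extra responders (*r* = 10% / 30% / 50%) | Shift in points |
|---|---|---|---|
| 1% | 2.0 | 0.2 / 0.6 / 1.0 | 0.1 / 0.3 / 0.5 |
| 3% | 6.1 | 0.6 / 1.8 / 3.1 | 0.3 / 0.9 / 1.5 |
| 5% | 10.2 | 1.0 / 3.1 / 5.1 | 0.5 / 1.5 / 2.5 |

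Alternatively, assume 20% to 40% total dropout spread evenly over six weeks. Then 204 × 0.20/6 = 6.8 to 204 × 0.40/6 = 13.6 subjects per arm stop in the last week. With *r* = 30% the shift is 100 × (0.20/6) × 0.30 = 1.0 to 100 × (0.40/6) × 0.30 = 2.0 points.

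**4. Between arms.** The shift in the treatment difference is 100 × (*d*₁*r*₁ − *d*₀*r*₀). With equal rates it is zero. With *d* = 3% in both arms and *r* = 50% on active against 10% on placebo, it is 1.5 − 0.3 = +1.2 points; with the response rates reversed it is -1.2. The inputs that fix the sign are not in the SAP.

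**The case against.** The strongest reply is that the specific sections already give one programmable answer. Sections 15.3.1.8 and 15.3.2 agree that only a missing value makes a non-responder. The 7.3 sentence stands in a general section that introduces discontinuation and missed assessments as causes of missing values. Read literally with no time point, it would make anyone who ever missed a visit a non-responder at every week, so it has to be read per visit. For the ranks, the instruction and the shell footnotes agree, and the conflicting words are an explanatory parenthesis. Section 6.3 also gives its purpose as tables and listings.

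Part of this stands: 7.3 does need a time point, and the operative rules are consistent with each other. It does not remove the conflict. Even read per visit, 7.3 names discontinuation separately from missed measurements. No passage ranks 15.3.2 above 7.3, and 6.3 expressly covers efficacy analysis. The sentence about the rank ANCOVA is untrue under 6.3.

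Two further objections are right and limit the point. Under Pattern 1, the time-to-failure analysis (Scenario #3, shell Table 14.2.1.2.3) counts discontinuation for any reason as failure, so a reader should not infer that the plan has no analysis that penalises every dropout. The responder endpoints are also other secondary endpoints without multiplicity adjustment.

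**Conclusion.** The SAP is wrong as written. Section 6.3 combined with 15.3.1.8, 15.3.2 and the Scenario #4 imputation rule contradicts 7.3 and the description of the rank ANCOVA in 15.1.4, and nothing in the document decides between them. This does not rest on any assumed rate.

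The size does. Over the assumed rates above, the Week 6 responder rate within an arm moves by about 0.1 to 2.5 percentage points, and about 2 to 10 subjects per arm (up to about 14 under 40% evenly spread dropout) escape the worst rank.

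A reader might infer that the shift favours the drug, for example if adverse-event dropouts on active treatment carry good scores and lack-of-efficacy dropouts on placebo do not. The SAP does not support that. The shift is within each arm, cancels if the arms behave alike, and can go either way if they do not. Nor does the point put the confirmatory results in question: the fix leaves the primary and key secondary MMRM as they are. The text should be reconciled before unblinding.

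**What to change.** **Preferred.** In 15.3.1.3, 15.3.1.8, 15.3.1.9, 15.3.2 and Scenario #4 of 15.1.4, and in the matching shell footnotes, add: *A subject who discontinued before the Week X visit is a non-responder at Week X, and receives the worst rank at Week 6, whether or not an early-termination value was assigned to that visit under Section 6.3.* In 7.3, state that the non-responder rule applies per time point. Section 15.3.2 must be amended with the others, or a new conflict replaces the old one. Keep the 6.3 shift for the MMRM.

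**Cost.** A sentence in each section and one flag from the disposition data. Responder rates become slightly lower. The same early-termination score will count as observed in the MMRM and as failure in the responder and rank analyses; a short note should say that this is intended.

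**Alternative.** If the sponsor prefers to count early-termination values, reword 7.3 and the 15.1.4 explanation so that both refer to subjects with no value at that visit after 6.3 has been applied, and drop the statement that all early discontinuations receive the worst outcome. This leaves the derivations unchanged but gives up the penalty for those who stop in the interval just before the visit.
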